review the participant’s medical information and provide an influenza diagnosis based on clinical judgement. If probable influenza is diagnosed, the 98point6 provider will confirm that antiviral treatment is appropriate. If appropriate, drug eligible study participant will subsequently receive a single dose of BXM delivered to their household via rapid delivery service for therapy initiation within 48 hours of symptom onset. Concurrently, the ill individual will collect a Study Day 0 nasal swab sample that will be mailed back to the laboratory for further testing. Additional nasal swabs will be collected at Study Day 2-3 and Study Day 5-7. If influenza is not diagnosed, the ill individual will provide one self-collected or parent/permanent legal guardian-collected nasal swab specimen that will be mailed back to the laboratory for further testing, and the household will remain enrolled and all study participants in the household will continue to self-monitor for presence of symptoms. Once an eligible study participant receives BXM, no additional household members will be eligible to receive BXM; the household will be able to continue monitoring for onset of symptoms, as well as self-testing and swabbing when symptoms develops, but the household will no longer be able to receive BXM delivery.

Figure 1. Study schema

Symptom Table

Feeling Feverish	Muscle or Body Aches
Headache	Rash
Sore Throat or Itchy/Scratchy Nose	Runny/stuffy nose
Feeling More Tired Than Usual	Muscle or body aches
Nausea or Vomiting	Increased trouble with breathing
Ear Pain or Ear Discharge	Diarrhea

The study is being conducted in the Seattle, WA area over one influenza season. The goal is to have 250 households comply with full study procedures. Of these, 25% are estimated to have an individual in the household diagnosed with influenza based on estimates from previous household studies.^{23, 28-29}

A table for influenza attack rates by household size is provided below.

Household attack rate	Total households enrolled	Primary cases	Secondary cases (mean household size 5)	Secondary cases (mean household size 4)	Secondary cases (mean household size 3)
25%	250	63	45-96	34-72	23-48
20%	250	50	36-76	27-57	18-38
10%	250	25	18-38	14-29	9-19
Mean household size includes case.					
Secondary attack rate 18-38%, secondary cases presented as a range based on these high and low bounds. ³⁰⁻³²					

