The University of Washington is the sponsor of the study which is supported by an anonymous funder who does not have any ownership over the management and conduct of the study, the data, or the rights to publish.

III. Objectives

The objective of the study is to measure the proportion of individuals who are initiated on antiviral therapy within 48 hours of symptom onset using a home-based self-test, followed by a telehealth consultation to diagnose influenza and home delivery of antivirals

Primary Outcome Measures

The primary outcome measure will be the proportion of eligible individuals who initiate antiviral therapy at home within 48 hours of symptom onset utilizing a home-based test and the telehealth app for influenza diagnosis and rapid home-delivery of antivirals. It will be calculated using binomial regression with log link, where the number of drug eligible influenza-diagnosed individuals, defined as the number of individuals eligible to receive BXM with both self-test positive influenza and laboratory-confirmed influenza, reporting administration of the study drug within 48 hours of symptom onset is divided by the total number of drug eligible individuals with both self-test positive influenza and laboratory-confirmed influenza.

Secondary endpoints:

- Proportion of individuals who test positive for influenza using the home-based test within 48 hours of symptom onset
- Proportion of individuals with a positive home-based influenza self-test who have a positive test confirmed by the central laboratory
- Sensitivity and specificity of a self-test compared to a laboratory-based molecular influenza test
- Proportion of individuals who are delivered antivirals within 48 hours of symptom onset
- Proportion of individuals who self-report administration antiviral therapy within 48 hours of symptom onset
- Symptom duration and severity among drug eligible and drug ineligible influenza-positive individuals
- Proportion of families with influenza infection diagnosed within 7 days of an index case (another influenza-positive household member)
- Viral quantity and duration of viral RNA detection among drug eligible and drug ineligible influenza-positive participants
- Proportion of drug ineligible study participants seeking medical care for respiratory illness symptoms
- Proportion of individuals who choose to take a self-test among those who are eligible to take a self-test

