4. Additionally, one week later, the ill individual will complete day 7 of the illness questionnaire, which will ask information about respiratory and systemic symptoms, recent travel history, and absenteeism in 7 calendar days following the onset of a cough in the ill participant.

Immediately following the onset of an acute cough or 2 or more respiratory symptoms in a drug eligible participant, the following procedures will occur:

1. The person will self-test for influenza using the prepositioned home-testing kit as long as the following criteria are met:
 - Symptom duration <48 hours
 - Cough present or 2 or more respiratory symptoms present
 - i. Qualification for receipt of study drug will be determined based on a review of medical information with the tele-health provider. If the individual meets the required criteria (symptom duration <48 hours) and is diagnosed with probable influenza by a healthcare provider, this will trigger subsequent delivery of the intervention, if deemed appropriate.
2. Next, the ill individual will collect a nasal swab sample via self-swab or parent/legal guardian-swab as soon as possible. These specimens will then be packaged and shipping back to the laboratory via a delivery service for testing and further characterization. Additionally, the ill individual will complete day 0 of illness questionnaire in REDCap, which will ask information about respiratory and systemic symptoms, recent travel history, and absenteeism.
3. Concurrently, the participant will connect with a provider via the tele-health app previously downloaded on their smartphone. The provider will review the participant's symptoms and determine whether influenza infection is likely to be the underlying cause of the symptoms. If probable influenza is diagnosed, the tele-health provider will prescribe a weight-based dose of BXM. If antiviral treatment is not deemed appropriate by the tele-health provider, this information will be documented in the post-visit Care Plan for the study participant and subsequently shared with the study team.
4. Next, the study pharmacy will be notified that the participant is being prescribed BXM.

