Initial Results: Once delivered to the laboratory, the boxes will be unpackaged and any errors that occurred during specimen return will be noted during this time in a spreadsheet accessible to all study staff. Next, the barcode for each specimen as well as a testing cartridge will be scanned into the multiplex PCR instrument (Cepheid) used for detection of influenza A/B or RSV in order to link testing results to each participant. Then, for each specimen, 300 μ L of UTM will be transferred to the testing cartridge and run on the Cepheid instrument. On the computer attached to the instrument, testing results are displayed in the GeneXpert Dx System qualitatively as a positive or negative for the three respiratory targets (influenza A, influenza B, and RSV), and quantitatively as Ct values. These results will then be manually entered into a centralized laboratory database, which can later be linked to clinical data for analysis.

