If the adverse event is considered by the medical expert team to be minor in severity, it will be logged in the centralized data capture system and a summary of such events will be reported to the DSMB. If the severity of the adverse event is considered to be moderate or severe by Principal and Co-Principal Investigators, it should be reported to the safety officer (DSMB) and the cognizant IRB immediately. All study-related SAEs will be reported to the IRB within 14 days.

The following are a list of anticipated and unanticipated adverse events we expect to be attributable to the study procedures or the intervention:

Anticipated Events: Mild-moderate systemic reactions, these include diarrhea, bronchitis, nausea, nasopharyngitis, and headache.

Unanticipated Events: By definition these are unexpected in terms of their nature, (see above for anticipated events) severity, and frequency, especially if they indicate that there may be greater risk of harm than previously recognized.

X. Definitions

Acute Respiratory Illness/infection (ARI): We will use the CDC definition of ARI that includes disease that typically involves the airways within the nose and throat and may or may not include fever. ARI is generally defined by the presence of two or more symptoms such as fever, cough, runny nose or nasal congestion, or sore throat. ARI is more sensitive (broader) than ILI to describe illness consistent with influenza because fever/feverishness are not required.

Drug eligible, influenza-infected study participant: A drug eligible study participant in the household that is diagnosed with influenza from a 98point6 provider based on a clinical review of the sick participant's symptoms.

Drug ineligible participant: A study participant in the household that is not able to receive BXM.

Influenza-like Illness in Adults and Adolescents (ILI): We will use the CDC definition of ILI that requires reported or measured fever ($>37.8^{\circ}\text{C}$) plus either cough or sore throat on one or more days preceding consultation with a tele-health physician.

Laboratory-confirmed influenza infection: We will use the CDC definition that is an individual who tests positive for influenza via an approved laboratory test, which will be the multiplex PCR (Cepheid) in this study.

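### The protocol's primary proportion drops self-test-positive people who have no usable mailed swab, so the on-time rate can be overstated if those not treated in time return swabs less often

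*Protocol*

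**What the plan says.** Protocol section III (Primary Outcome Measures) defines the numerator as drug-eligible, doubly positive people "reporting administration of the study drug within 48 hours of symptom onset". That number "is divided by the total number of drug eligible individuals with both self-test positive influenza and laboratory-confirmed influenza". Section X (Definitions) treats infection as laboratory-confirmed when a person "tests positive for influenza via an approved laboratory test, which will be the multiplex PCR (Cepheid) in this study".

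The PCR is not run on the self-test sample. Under section II (Study design), "the ill individual will collect a Study Day 0 nasal swab sample that will be mailed back to the laboratory for further testing". Section V (Onset of Symptoms) adds: "These specimens will then be packaged and shipping back to the laboratory via a delivery service". Telehealth contact runs in parallel with this: "Concurrently, the participant will connect with a provider via the tele-health app previously downloaded on their smartphone".

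The protocol foresees that swabs may fail to arrive or arrive in poor order. The Withdrawal criteria let a member stop giving samples while still giving symptom data. In section VI (Initial Results), "any errors that occurred during specimen return will be noted during this time in a spreadsheet accessible to all study staff". Neither document says how a self-test-positive person with no valid PCR result is classified in the primary analysis.

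Other descriptions of the target group differ. Protocol section XI refers to drug-eligible people with an influenza diagnosis, and defines n as those testing positive for flu. SAP section B6 counts successes among participants with cough and a positive self-test, without laboratory confirmation. It divides by all influenza-free participants at baseline and scores late or never-treated participants as failures.

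**The concern.** The primary result is meant to show how often a home strategy gets drug into infected people in time. Someone who self-tests positive and then stops, with no swab, no telehealth visit and no drug, is the plainest failure of that strategy. Under the protocol's rule this person is deleted, because a missing PCR has the same effect as a negative one.

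Returning the swab, opening the app and taking the drug are all tasks for the same ill person at home after the self-test. One disengagement can remove both the treatment and the evidence that it was missed. The proportion is then conditional on completing a further study task, and its confidence interval carries no sign of the selection.

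**Working it through.** **1. The plan's own figure.** Protocol section XI: 250 households × 25% = 62.5, taken as 63. The worst-case half-width is 1.96 × 0.5/√63 = 0.1235, which matches the stated 0.12. The calculation makes no allowance for unreturned swabs. With 57 or 50 evaluable people it becomes 0.130 or 0.139.

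**2. Who is counted.** Among drug-eligible, truly infected, self-test-positive people:

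| | Usable swab returned | No usable swab |
|---|---|---|
| Dosing within 48 h reported | success | dropped |
| Late, never treated, or not reported | failure | dropped |

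The right-hand column is harmless only if its success rate equals that of the left-hand column.

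**3. Mixture calculation.** The documents give neither a return rate nor an expected success rate, so the values here and in steps 4 and 5 are assumptions. Let m be the fraction without a usable swab, with 85% on time in returners and 50% in non-returners. The rate in all self-test positives is 0.85(1 − m) + 0.50m.

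- m = 0.10: 0.765 + 0.050 = 0.815, so a reported 85% is 3.5 points too high
- m = 0.20: 0.680 + 0.100 = 0.780, 7.0 points too high
- m = 0.30: 0.595 + 0.150 = 0.745, 10.5 points too high

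All three are below the stated 0.12. That figure is a ceiling set at p = 0.5; at p = 0.85 and n = 63 the half-width is 1.96 × √(0.85 × 0.15/63) = 0.088.

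**4. Direction.** Let p be the true on-time rate, and rS and rF the probabilities that a success and a failure return a usable swab. The observed rate is p·rS / [p·rS + (1 − p)·rF]. With p = 0.70:

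| rS | rF | Observed | Bias |
|---|---|---|---|
| 0.90 | 0.90 | 0.700 | 0 |
| 0.95 | 0.80 | 0.735 | +0.035 |
| 0.95 | 0.60 | 0.787 | +0.087 |
| 0.95 | 0.40 | 0.847 | +0.147 |
| 0.80 | 0.95 | 0.663 | −0.037 |

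The sign depends entirely on which group returns fewer swabs. Only the most extreme row exceeds 0.12.

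**5. Bounds without an assumed direction.** Take 63 self-test positives and about 70% success among returned swabs.

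- 6 missing: observed 40/57 = 0.702; range 40/63 = 0.635 to 46/63 = 0.730
- 13 missing: observed 35/50 = 0.700; range 35/63 = 0.556 to 48/63 = 0.762

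**6. Protocol against SAP.** A self-test-positive person with cough, no swab and no treatment is absent from the protocol's proportion. In the SAP's outcome definition the same person is a failure, provided that the SAP B1 exclusion for a missing symptom questionnaire does not apply. The SAP's ratio is nevertheless on another scale, because its denominator includes everyone influenza-free at baseline.

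**The case against.** A reader might infer that the rate is overstated. The documents do not support that. Swab and telehealth visit are concurrent, so an untreated person can return a swab. A treated person may withdraw from sampling alone. The gift is $30 for drug receipt but $5 per swab sequence. All of this leaves room for non-return among successes, which would bias the rate downward. A swab returner who took the drug but did not record it also lowers the rate. This part of the objection stands: upward bias is the more plausible direction, because one disengagement affects both tasks, but it is not established.

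A reader might also infer that both documents discard these people. They do not, since the SAP's success and failure definitions need no laboratory result.

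The target is a further objection. Confirmation properly removes false-positive self-tests, and self-test accuracy is itself a secondary endpoint, so the proportion in all self-test positives is a different estimand. This stands as far as valid PCR negatives go. It does not justify treating an absent result as a negative one.

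Finally, the protocol works to limit non-return through a baseline swab trial run, prepaid return materials, gift cards for returned swabs and a willingness-to-comply criterion. It also lists secondary endpoints on delivery and self-reported intake within 48 hours that do not mention laboratory confirmation. These measures should reduce the loss, but they neither classify those who are lost nor bound their effect, and those endpoints name no denominator.

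**Conclusion.** The point holds as a conditional one. The protocol's rule removes self-test-positive people without a usable swab, including any who disengaged and were never treated. The primary proportion can therefore be overstated if non-return is more common among those not treated in time. Neither direction nor size can be read from the documents.

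Under the assumed 85% and 50% on-time rates with 10% to 30% missing, the overstatement is 3.5 to 10.5 points, below the stated 0.12 half-width but not reflected in it. Equal return gives zero bias; return of 80% in successes and 95% in failures understates a true 70% by 3.7 points. Separately, and without any assumption, the protocol and SAP disagree on the denominator and on whether laboratory confirmation is required. The change is cheap and worth making for a pilot whose single primary result is this proportion.

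**What to change.** In protocol sections III and XI and in SAP B6:

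- Remove from the denominator only drug-eligible, self-test-positive people with a valid negative Day 0 PCR. Keep those with a missing or unusable swab, scored from the dosing record and delivery log.
- Report the doubly positive set as a sensitivity analysis with bounds for missing PCR. The worst case adds only missing-PCR people not treated in time; the best case adds only those treated in time.
- Tabulate swab-return rates by treatment status, so that the direction of any selection can be seen.
- Align the SAP denominator with the protocol's, and check that the SAP B1 questionnaire exclusion does not remove the same people again.

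Later swabs should not define the primary denominator. Under Table 1 and section VI, Day 2-3 and Day 5-7 swabs come only from drug-eligible people diagnosed by the telehealth provider. Accepting any swab would give that group three chances of confirmation and undiagnosed people one.

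The cost is wording and one extra table, using dosing times and delivery logs already collected. The downside is that some false-positive self-tests without a PCR result stay in the denominator; the sensitivity analysis shows how much that matters.
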